## 2.2 Trial Diagram

The trial diagram is depicted in Figure 1.

Figure 1: Trial Diagram

### 3.0 OBJECTIVE(S) & HYPOTHESES

#### 3.1 Primary Objective(s) & Hypotheses

- (1) **Objective:** Evaluate the safety and tolerability of V920 in HIV-infected adults and adolescents.
- (2) **Objective:** Evaluate the immunogenicity of V920 via ZEBOV- specific antibody responses induced by V920 in HIV-infected adults and adolescents.

#### Primary Hypotheses:

- 1) The geometric mean titer (GMT) of GP-ELISA in V920 vaccinated HIV-infected adults and adolescents will be superior to the GMT of the GP-ELISA in placebo vaccinated HIV-infected adults at Day 28 in Cohorts 1-5 combined.
- 2) The geometric mean titer (GMT) of GP-ELISA in V920 vaccinated HIV-infected adults and adolescents will be superior to the GMT of the GP-ELISA in placebo vaccinated HIV-infected adults and adolescents Day 28 after the last dose of vaccine (equivalent to Day 84 from first dose) in Cohort 5

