#### 3.2 Secondary Objective(s)

- (1) **Objective:** Evaluate VSV viremia and shedding after administration of V920.
- (2) **Objective:** Evaluate ZEBOV-specific antibody responses induced by V920 through D180 and D365.
- (3) **Objective:** Evaluate the impact of V920 on HIV viral load, CD4 counts, and CD4/CD8 ratio.
- (4) **Objective:** Evaluate the safety and tolerability of two doses of V920 in HIV-infected adults and adolescents administered 56 days apart.
- (5) **Objective:** Evaluate the immunogenicity of two doses of V920 administered 56 days apart via ZEBOV-specific antibody responses induced by V920 at D28 post-dose 2 in HIV-infected adults and adolescents.

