#### **4.2.2.2 Vaccine Dose for This Trial**

One dose of  $\geq 2 \times 10^7$  pfu of the study vaccine or placebo will be administered at D0 in all Cohorts. In Cohort 5, a second dose of matching vaccine ( $\geq 2 \times 10^7$  pfu/ml) or placebo will be administered at Day 56. The rationale for assessing a second dose in HIV positive subjects is to access whether a second dose will provide a greater immune response or a response in a greater proportion of subjects in case one dose is less immunogenic in HIV positive subjects than in non-HIV positive subjects assessed in other studies. The 56 day interval is based on the interval utilized in other studies that include non-HIV positive adults and children.

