#### **4.2.3 Rationale for Endpoints**

##### **4.2.3.1 Immunogenicity Endpoints**

1. Primary endpoints:
  - a. ZEBOV-specific antibody responses measured by ELISA and neutralization on Day 28 in Cohorts 1-5 combined.
  - b. ZEBOV-specific antibody responses measured by ELISA and neutralization on Day 28 after the last dose of vaccine (equivalent to Day 84 from first dose) in Cohort 5.
2. Secondary endpoints:
  - a. ZEBOV-specific antibody responses measured by ELISA and neutralization on Day 28 in Cohort 5.
  - b. ZEBOV-specific antibody responses measured by ELISA and neutralization on Days 180 and 365 after the first dose of vaccine.

The V920 vaccine candidate is a live recombinant vesicular stomatitis virus (VSV) expressing the glycoprotein (GP) of Zaire Ebola virus (ZEBOV). Two independent assays are currently being utilized in the clinical development program to clinically evaluate the immunogenicity of V920:

- GP-ELISA measures the total IgG antibody response and can also be correlated to the plaque reduction neutralization assay (PRNT) titer result.
- Plaque reduction neutralization assay (PRNT) is a functional assay and a gold standard platform in the field for quantitating the neutralizing antibody response elicited by the vaccine.

If in the clinical development program one assay is found to be sufficient to characterize the immune response, use of the assay that does not add value may be discontinued.

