### 8.2.5 Statistical Methods

#### 8.2.5.1 Statistical Methods for Immunogenicity Analyses

Immunogenicity summaries will include: means and 95% CIs of the Geometric Mean Titers (GMT) and Geometric Mean Fold Increase from baseline (GMFI) of ZEBOV-specific antibody responses at baseline and Day 28, Day 84 (Cohort 5 only), Day 180, and Day 365.

Immunogenicity summaries will include: counts, percentages, and 95% CIs of subjects who achieve seroconversion (e.g. 4-fold increase) for ZEBOV-specific antibody responses at baseline and Day 28, Day 84 (Cohort 5 only), Day 180, and Day 365.

Immunogenicity summaries will include: counts, percentages, and 95% CIs of subjects who achieve seroprotection for ZEBOV-specific antibody responses at baseline and Day 28, Day 84 (Cohort 5 only), Day 180, and Day 365 based on correlate of protection thresholds, if found. Fisher's exact (primary) or Chi-square test (secondary if proportion size warrants) will be used to compare the frequency of ZEBOV-specific antibody responses and Student's t (primary) or Wilcoxon rank-sum test (secondary if not normally distributed) will be used to compare ZEBOV-specific GMT ZEBOV-specific antibody between treatment groups. All hypotheses will be evaluated using two-sided tests at  $\alpha = 0.05$ . Superiority of immune response will be defined as a statistically significant difference.

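### Cohort 5's only hypothesis compares two doses with placebo, so it cannot show what the second dose adds, and the antibody sample drawn before dose 2 (Day 56) has no planned analysis

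*Combined protocol and SAP*

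**What the plan says.** Section 4.2.2.2 gives the reason for dose 2: to learn "whether a second dose will provide a greater immune response or a response in a greater proportion of subjects". The sentence goes on to tie this to the possibility that one dose works less well in HIV-positive subjects than it did in HIV-negative subjects elsewhere.

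The objectives and endpoints do not carry that comparison forward:

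- Primary Hypothesis 2 (Section 3.1) is superiority of the V920 GMT over the placebo GMT at "Day 28 after the last dose of vaccine (equivalent to Day 84 from first dose) in Cohort 5".
- Secondary objective 5 (Section 3.2) is to "Evaluate the immunogenicity of two doses of V920 administered 56 days apart via ZEBOV-specific antibody responses induced by V920 at D28 post-dose 2". It names no comparator.
- Section 4.2.3.1 adds a secondary endpoint, "ZEBOV-specific antibody responses measured by ELISA and neutralization on Day 28 in Cohort 5", without a contrast against Day 84.
- Section 8.2.5.1 gives a t-test, with Wilcoxon as the alternative, that "will be used to compare ZEBOV-specific GMT ZEBOV-specific antibody between treatment groups". Summaries of GMT, fold increase from baseline (GMFI), seroconversion and seroprotection are planned "at baseline and Day 28, Day 84 (Cohort 5 only), Day 180, and Day 365". Section 8.1 has the same list.

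Day 56 is in none of these lists, although the Cohort 5 flow chart (Section 6.0) draws antibody that day before dose 2. Section 8.2.2 restates Hypothesis 1 only.

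**The concern.** The rationale poses a question of two doses against one, while the test is two doses against none. Any antibody left from dose 1 on Day 84 counts towards success, so a positive Hypothesis 2 is compatible with a large dose-2 effect, a small one or none. GMFI on Day 84 is measured from baseline and likewise combines both doses.

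The value that would isolate the boost, the titre just before dose 2, is collected but assigned to no analysis. Cohorts 1-4 have antibody draws at baseline and Days 28, 180 and 365 only, so they offer no one-dose reference on Day 84. Followed as written, the plan gives Cohort 5 subjects a second dose and leaves the question behind it without an inferential contrast.

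A lesser matter concerns the endpoint "ZEBOV-specific antibody responses measured by ELISA and neutralization on Days 180 and 365 after the first dose of vaccine". It does not say whether one-dose and two-dose recipients are reported apart, and the subgroups in Section 8.2.8 are CD4 count and age, not number of doses.

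**Working it through.** **Inputs.** From Section 8.2.7: 40 V920 and 10 placebo per cohort, 10% dropout (36 and 9 evaluable), SD 1 on the log scale, two-sided 5%. Assumed, because the documents do not give them: the geometric mean ratio (GMR) over placebo still left from dose 1 on Day 84, and the within-subject correlation ρ of log titres.

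**1. The plan's own figure.** Two-sample t-test, df = 43, SE = √(1/36 + 1/9) = 0.373, noncentrality = ln(GMR)/0.373.
- GMR 2.9: 1.065/0.373 = 2.86, power 79.7% (plan: 80%).
- GMR 3.4: 1.224/0.373 = 3.28, power 89.4% (plan: 90%).

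The figures reproduce with SD 1 taken as natural log.

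**2. Hypothesis 2 if dose 2 adds nothing.** The same formula applies, with the GMR now being what dose 1 alone leaves on Day 84.

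| Residual dose-1 GMR | Noncentrality | Chance Hypothesis 2 succeeds |
|---|---|---|
| 1.5 | 1.09 | 19% |
| 2.0 | 1.86 | 44% |
| 2.9 | 2.86 | 80% |
| 3.4 | 3.28 | 89% |
| 5 | 4.32 | 99% |

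A simulation of 5,000 trials with no dose-2 effect gave 80% at 2.9 and 99% at 5. Section 8.2.7 quotes one detectable GMR for every cohort, whether it receives one dose or two, so the plan's power figure makes no distinction either.

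**3. Is the Day 56 sample really drawn?** The neutralising-antibody row of the Cohort 5 flow chart marks Day 56 with the before-vaccination footnote. The volumes agree: haematology 4 + chemistry 8 + VSV 5 + viral load 8 + CD4/CD8 4 = 29 mL, and adding 20 mL for antibody gives the stated total of about 49 mL.

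**4. What a paired contrast would deliver.** For 36 V920 completers, SD of the log difference = √(2(1−ρ)), SE = SD/6, and the 95% CI multiplier is exp(t₀.₉₇₅,₃₅ × SD/6).

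| Assumed ρ | SD of difference | Ratio, 80% power | Ratio, 90% power | CI multiplier (×/÷) |
|---|---|---|---|---|
| 0.3 | 1.18 | 1.77 | 1.93 | 1.49 |
| 0.5 | 1.00 | 1.62 | 1.74 | 1.40 |
| 0.7 | 0.77 | 1.45 | 1.54 | 1.30 |
| 0.9 | 0.45 | 1.24 | 1.28 | 1.16 |

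With no change in titre from Day 56 to Day 84, the paired test rejected in 4.9% to 5.3% of simulated trials (ρ = 0.7), while Hypothesis 2 succeeded in 80% to 100% of the same trials (residual GMR 2.9 to 10).

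**5. Days 180 and 365, illustration only.** Cohort 5 supplies 40 of 200 V920 recipients, or 20%. If all were pooled, a residual boost of 2-fold would raise the pooled GMT by 2^0.2 = 1.149 (15%), and one of 4-fold by 4^0.2 = 1.320 (32%). Both boosts are assumed.

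**The case against.** **The question is conditional and appears only as a dose rationale.** The formal objectives are to evaluate the two-dose regimen, and Hypothesis 2 validly tests what it states. This stands, and it lowers the severity. It does not supply an analysis for the stated reason for dose 2.

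**The increment is partly recoverable.** GMFI is planned on Days 28 and 84, and in the same subjects GMFI(D84)/GMFI(D28) is exactly the within-subject fold ratio. So a reader who infers that the plan yields nothing on the increment goes too far. What is missing is the paired interval and the Day 56 value; Day 28 is not the level just before dose 2.

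**A reader might infer that Hypothesis 2 is bound to succeed.** The documents do not support that. Section 4.1 calls single-dose immunity only likely to be durable, and the 100% seroconversion by 28 days in Section 4.1.3 comes from the Phase 1 programme, not from this HIV-infected population. If one dose is weak, success without a dose-2 effect is far from assured (44% at a residual GMR of 2.0).

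**A reader might infer that late titres will be pooled across regimens.** No passage says so. Where cohorts are combined for a hypothesis, at Day 28, the plan states it.

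**The paired ratio is not a clean effect of dose 2.** Number of doses is not randomised. D84/D56 includes any natural rise or fall in dose-1 titre over those 28 days, and placebo recipients cannot show that drift. Comparisons of Cohort 5 with Cohorts 1-4 are between sequentially enrolled groups. Both limits stand and belong in the label of the analysis.

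**Conclusion.** The point holds and should be fixed; it does not invalidate the primary tests. A significant Day 84 result against placebo cannot separate a dose-2 effect from persisting dose-1 antibody. If dose 2 adds nothing, success still has probability of about 44%, 80% or 99% at a residual dose-1 GMR of 2.0, 2.9 or 5. These figures rest on the plan's SD, dropout and sample size, and on a residual GMR that the documents leave open.

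The Day 56 sample is drawn and unused in the SAP, and no paired interval is planned for any increment. A paired estimate would be informative: 80% power at a fold ratio between 1.77 and 1.24, depending on the assumed correlation. The late time points need only clarification of how they will be presented; the 15% and 32% figures are illustrations, not predictions.

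**What to change.** In Sections 8.1 and 8.2.5.1:

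1. Add Day 56 (Cohort 5, before dose 2) to the antibody time-point lists.
2. For Cohort 5 V920 recipients, add the paired geometric mean fold ratios D84/D56 (main) and D84/D28 on log titre, with 95% CIs. Label them as within-subject, non-randomised estimates that include any natural change in dose-1 titre between the two days, which the placebo arm cannot show. Report the paired change in responders descriptively, because it says little if nearly everyone responds to dose 1.
3. Present Days 180 and 365 separately for one-dose (Cohorts 1-4) and two-dose (Cohort 5) recipients. Any ratio between them should be descriptive, since the cohorts are sequential and not randomised against each other.
4. State that Hypothesis 2 against placebo is not evidence of second-dose benefit.

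The cost is SAP wording and a few more tables, plus an estimate that must carry a time-trend caveat. There are no new samples, visits or subjects. Section 8.0 allows non-confirmatory analyses to be changed in a supplemental SAP before final database lock; specifying these before unblinding keeps them from being post hoc.

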#### 3.2 Secondary Objective(s)

- (1) **Objective:** Evaluate VSV viremia and shedding after administration of V920.
- (2) **Objective:** Evaluate ZEBOV-specific antibody responses induced by V920 through D180 and D365.
- (3) **Objective:** Evaluate the impact of V920 on HIV viral load, CD4 counts, and CD4/CD8 ratio.
- (4) **Objective:** Evaluate the safety and tolerability of two doses of V920 in HIV-infected adults and adolescents administered 56 days apart.
- (5) **Objective:** Evaluate the immunogenicity of two doses of V920 administered 56 days apart via ZEBOV-specific antibody responses induced by V920 at D28 post-dose 2 in HIV-infected adults and adolescents.

#### 3.3 Tertiary Objective(s)

- (1) **Objective:** Evaluate Ebola-specific CD8 T cell responses
- (2) **Objective:** Evaluate B-cell repertoire
- (3) **Objective:** Evaluate the impact of V920 on HIV viral reservoir

## 4.0 BACKGROUND & RATIONALE

### 4.1 Background

Refer to the Investigator's Brochure (IB) for detailed background information on V920.

Ebolaviruses (EBOV) are members of the Filoviridae and are known primarily as the underlying cause of severe viral hemorrhagic fevers with disturbingly high case fatality rates. Between 1994 and the present, there have been many EBOV outbreaks (refer Table 1) affecting mostly central Africa, with two large outbreaks in 1995 in Kikwit, DRC and in Gulu, Uganda in 2000-2001.

The West African outbreak significantly exceeds all previous outbreaks in geographic range, number of patients affected and in disruption of typical activities of civil society. The West African Ebola outbreak was first recognized in Guinea, and then spread to Liberia and Sierra Leone, with a few imported cases resulting in some spreading in Nigeria, Mali, Senegal, U.S., UK and Spain. The vast majority of cases are from Guinea, Liberia and Sierra Leone. The epidemic peaked from Aug-2014 to Oct-2014, and as of 25-Nov-2015, it has caused over 28,000 reported cases and 11,000 deaths reported by the WHO (Figure 2).

[figure not shown]
The disease affects both adults and children, although most cases are aged 20 to 50 years. The incubation period ranges from 2 to 21 days, with an average of 10 days in patients aged 16 to 44 years, 11 days in patients aged 45 years or older, and a shorter average in children (7 days in children younger than 1 year and 10 days in children aged 10 to 15 years).

Table 1: Ebolavirus Outbreaks

Viral species	Year	Outbreak location	# of human cases (% fatality)
Zaire Ebolavirus	1976	Yambuku, Zaire (DRC)	318 (88%)
	1977	Tandala, Zaire (DRC)	1 (100%)
	1994	Ogooue-Invindo province, Gabon	51 (60%)
	1995	Kikwit, Democratic Republic of Congo	315 (79%)
	1996	Mayibout, Gabon	37 (57%)
	1996	Booue, Gabon and Johannesburg, South Africa	61 (74%)
	2001-02	Ogooue-Invindo province, Republic of Congo	124 (79%)

	2002-03	Cuvette region, RC and Ogooue-Invindo province, Gabon	143 (90%)
	2003	Mboma and Mbandza, Republic of Congo	35 (83%)
	2005	Etoumbi and Mbomo, Republic of Congo	12 (75%)
	2007	Kasai Occidental province, Democratic Republic of Congo	249 (73%)
	2008/2009	Democratic Republic of the Congo	32 (47%)
	2014	Democratic Republic of the Congo	66 (72%)
	2014-2016	West Africa including Guinea, Sierra Leone, Liberia	28,652 (40%)
	2017	Democratic Republic of the Congo	17 (23%)
Sudan Ebolavirus	1976	Nzara, Maridi, Tembura, Juba, Sudan	284 (53%)
	1979	Nzara, Yambio, Sudan	34 (65%)
	2000-01	Gulu, Masindi, Uganda	425 (53%)
	2004	Yambio, Sudan	17 (41%)
	2011	Uganda (Luwero District)	1 (100%)
Taï Forest	1994	Tai forest, Ivory Coast	1 (0%)
	1995	Liberia, Liberia	1 (0%)
Reston Ebolavirus	1989	Reston, USA	4 (0%)
	1992	Siena, Italy	0
	1996	Alice, Texas	0
	2008	Phillipines	0
Bundibugyo Ebolavirus	2007/2008	Uganda	131 (37%)

Figure 2: Total suspected, probable, and confirmed cases of Ebola virus disease in Guinea, Liberia, and Sierra Leone, March 25, 2014-February 14, 2016, by date of WHO Situation Report, n=28603.

By WHO Situation Report

Source: <http://www.cdc.gov/vhf/ebola/outbreaks/2014-west-africa/cumulative-cases-graphs.html>

### Therapies for Filovirus infections

Treatment of Ebola hemorrhagic fever is mainly supportive, involving fluid and electrolyte replenishment and pain reduction. Specific treatments are under development. Convalescent plasma was used in a limited number of patients during the Kikwit 1995 ZEBOV outbreak, but its success was disputable. Passive immunization with hyperimmune horse serum delayed but did not prevent death in cynomolgus macaques. Monoclonal antibody treatment was successful in rodent models, but failed in preliminary NHP studies, indicating a possible evasion of antibody neutralization. All of the abovementioned studies used single monoclonal antibody clones, which may not be sufficient to control infection.

During the recent outbreak, experimental therapies including a cocktail of 3 monoclonal antibodies (ZMapp, Mapp Biopharmaceutical), lipid encapsulated siRNA (small interfering RNA, TKM-Ebola, Tekmira Pharmaceuticals Corp), and two antiviral drugs (brincidofovir and favipiravir) have been employed in individual patients. Although the efficacy of these treatments in these patients is not clear, they have been shown to be successful in animal

studies. Treatment with the optimized ZMapp cocktail rescued 100% of rhesus macaques when treatment was initiated up to 5 days after lethal EBOV challenge. The Tekmira siRNA product similarly showed high-grade protection against lethal filovirus infection when NHP were treated up to 3 days after challenge. The rVSVΔG-ZEBOV-GP vaccine may also play an important role in preventing the onset of the Ebola virus disease (EVD) in situations where the precise time of exposure were known, and the vaccine could be applied early after exposure.

A preventive vaccine, in contrast, could be used to protect individuals at high risk in advance of exposure, such as persons traveling to or residing in endemic or epidemic settings, and could be used for outbreak control at a population level to interrupt transmission. Since the rVSVΔG-ZEBOV-GP vaccine elicits rapid and likely durable immunity after a single dose, it has important potential for use in this context, as well as for the indication of post-exposure prophylaxis after recognized, high-risk exposure.

### **Vesicular stomatitis virus as a vaccine vector**

VSV belongs to the family Rhabdoviridae, genus Vesiculovirus. These are bullet-shaped, single-stranded, negative-sense RNA viruses containing five genes, one of which is the viral GP. In the U.S., the two most common serotypes are VSV-New Jersey and VSV-Indiana. VSV cause significant disease in pigs, cattle, and horses, primarily manifesting as crusting and vesiculation of the mucous membranes and skin, and lameness due to involvement of the coronary bands of the hoof. The virus is maintained in nature in a cycle involving sandflies and rodent reservoirs. It is also transmitted between livestock by direct contact, likely including droplet spread and fomites, as well as mechanically by non-biting houseflies and face flies. Pre-existing immunity to VSV is not prevalent in humans in the U.S., and VSV does not circulate outside the Western Hemisphere; therefore it is not expected to be a significant factor in a potential vaccination campaign in the U.S. or in parts of Africa with VSV-based vaccines. Moreover, in VSV vaccines where the viral GP is replaced with GPs of other viruses, the impact of pre-existing anti-VSV neutralizing antibodies is theoretically minimized.

VSV virus can be transmitted to humans who come in close contact with infected animals. The incubation period is most commonly 3 to 4 days. The most common clinical manifestation is a limited, 3- to 5-day flu-like illness. In rare cases, humans can manifest vesicles on the oropharyngeal, nasal mucosa or skin. Human deaths secondary to infection have not been reported; however, encephalitis was reported in a single case of a 3-year old child secondary to VSV-Indiana infection. As there is only one case report in the literature, the risk of central nervous system infection following VSV infection is undoubtedly rare. In some areas of tropical America, a high seroprevalence to VSV has been reported without recognized disease. Thus, it is likely that the ratio of infection to illness with VSV is high.

The V920 construct used in the clinical trials was derived from the VSV-Indiana serotype. As described above, the rVSV-based vector used in this vaccine lacks the VSV GP, the viral determinant for neurotropism and pathogenicity, rVSVΔG-ZEBOV-GP has approximately 33% slower growth kinetics than wild-type VSV in Vero cell cultures, contributing to

#### 4.1.1 Pharmaceutical and therapeutic background

##### rVSVΔG-ZEBOV-GP AS A CANDIDATE VACCINE FOR EBOLA ZAIRE DISEASE

The rVSVΔG-ZEBOV-GP vaccine is a live attenuated recombinant virus consisting of a single recombinant VSV isolate (11481 nt, strain Indiana) with the gene for the *Zaire ebolavirus* GP (ZEBOV GP), Kikwit strain replacing the gene for the VSV GP, which has been deleted. This results in a VSV backbone with the ZEBOV GP constituting the envelope of the virus. As for similar chimeric vaccines, the substitution of the native virus GP genes with a heterologous GP leads to significant attenuation of a virus. The ZEBOV GP on the surface of the virus may narrow the cell tropism of the recombinant virus. The substitution of the heterologous Ebolavirus GP does not perturb the proper assembly of the virus particle, and the recombinant vaccine resembles the native VSV bullet structure in electron micrographs (Figure 3). Refer to the Investigator's Brochure (IB)/approved labeling for detailed background information on V920.

Figure 3: (A) A single-stranded, negative-sense RNA encoding 5 transcriptional units: N (nucleoprotein), P (phosphoprotein), M (matrix), G (glycoprotein), and L (polymerase).

rVSVΔG-ZEBOV-GP was generated by deleting the VSV G gene and inserting the ZEBOV GP gene in the new transcriptional unit after the VSV M gene. (B) Electron micrograph of the WT VSV and rVSVΔG-ZEBOV-GP.

